### 5.1.2 Additional Treatment Period (ATP) for Qualifying Patients Only

For the purposes of clarity and efficiency, rather than continuing to present chronological days/weeks, visits are presented as 'ATP Day 0', followed by, 'ATP Days 28, 56, 84', etc. Qualifying patients will 're-start' IMG-7289 on ATP Day 0, with dose titration continuing as per the Titration Rules table (Section 7.2.3.2); there should be no interruption in dosing (Day 168 = Day 0 of the next ATP). Additional dose-titration may occur in consultation with the Medical Monitor.

During the ATP, qualifying patients will return to the clinic monthly for study assessments (ATP Days 0, 28, 56, 84, 112, 140 and 168). It is anticipated that patients continuing in the ATP will have already achieved a stable dose, with bi-weekly visits no longer necessary. For the exceptional patient whose dose has not stabilized, bi-weekly visits may continue at the PI's discretion. On Day 168, patients will undergo the same procedures and assessments as per ITP Day 168, including MRI or CT (if patient is not a candidate for MRI), and bone marrow sampling. Prior to or at the Day 168 visit, but ideally at the Day 140 visit for logistical purposes, a 'qualification' assessment will again be made to determine whether the patient is continuing to derive clinical benefit, thereby re-qualifying for continued treatment in the ATP. The ATP is iterative and may repeat (ATP1, ATP2, etc.), without interruption in dosing, as long as the patient continues to qualify.

**Note:** In Germany, use of computerised tomography (CT) is not permitted for patients unable to undergo magnetic resonance imaging (MRI). Only MRI is permitted for study purposes.

Patients not deriving clinical benefit, or who achieve CR, PR or CI and subsequently relapse (Section 16.7), the equivalent of treatment failures, will discontinue IMG-7289 and undergo EoT, pre-EoS and EoS visits.

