Patients enrolled in the Phase 1/2a portion of study are treated in the ITP daily for 85 days; if qualified, they may continue to the ATP after a brief washout period, and be treated daily for an additional 85 days. Patients enrolled in the Phase 2b portion of study are treated in the ITP daily for 169 days; if qualified,

they may continue directly to the ATP with no washout period, and be treated daily for an additional 169 days.

All patients will undergo follow-up period visits, including an End-of-Treatment (EoT) visit on the day of last dose or as soon as possible thereafter, a pre-End-of-Study (EoS) visit approximately 14 days post last dose, and an End-of-Study (EoS) visit approximately 28 days post last dose. Patients that do not enter the Additional Treatment Period, or discontinue early, will undergo follow-up, beginning with an EoT visit.

Patients will be followed closely throughout the study for both Adverse Events (AEs) and signs of toxicity by frequent monitoring of clinical signs and symptoms and by peripheral blood and urine analyses. Pharmacodynamic effects will be closely monitored by frequent haematology assessments of peripheral blood, and requisite bone marrow aspirates and biopsies. Throughout dosing, transfusions may be administered if needed in accordance with standard institutional guidelines.

B. Study Population

The patient population will consist of men and women age 18 or older who have been diagnosed with intermediate-1, intermediate -2 or high-risk primary myelofibrosis (PMF), post-polycythaemia vera myelofibrosis (PPV-MF), or post-essential thrombocythaemia myelofibrosis (PET-MF). Eligible patients who have signed informed consent must have had no prior treatments within a specified period of time and met pre-specified laboratory values for selected parameters, in addition to multiple other required eligibility criteria.

C. Sample Size Predictions

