If sufficient patients within a phase and cohort have visits that are performed off-schedule, and there is concern that summary by designated visit within period will be misleading due to comparison of assessments that have not had comparable treatment duration within that period, then visit windowing may be utilized for data summarization. In that case, visit windows will be defined by establishing the expected schedule for the dose/cohort, and establishing boundaries for each window as the midpoint between the previous expected visit day and the next expected visit day. Assessments will be slotted for summarization according to the visit windows, rather than the visit designated in the eCRF. If more than one assessment occurs within a particular window, then the assessment closest to the expected visit day will be used. If more than one such assessment exists, then the assessment whose visit designation in EDC is closest to the expected visit designation will be used. If windowing is applied for a given type of assessment, this will be indicated in the footnote of the summary table and the corresponding listing, and the listing will indicate both the visit designation from EDC and the visit window in which the assessment is included.

This methodology may be applied to summaries of laboratory data, vital signs data, and/or symptom scores. As assessment schedules may differ for these assessments, windows may be parameter type-specific.

K. Analysis Populations

Only the Safety population will be considered as analysis population for performing the various analyses. All enrolled patients who received at least one dose of IMG-7289 will be included in the Safety population.

Patients having no post-baseline disease assessment will be defined as NE (not evaluable).

L. Subgroups of Analysis Populations

The summaries and listings will be separated by the starting dose, and type of disease within starting dose. Summaries will include an “All Patients” category for each starting dose, as well as an “All Patients” category for the entire set of patients in the analysis set.

Categories for starting dose are: Phase 1/2a - 0.25 mg/kg/d (amendments 1, 2 and 3); Phase 2b - 0.5 mg/kg/d (amendments 4, 5); and Phase 2b - 0.6 mg/kg/d (amendment 6).

Categories for type of disease are: primary myelofibrosis (PMF), post-polycythaemia vera myelofibrosis (PPV-MF), or post-essential thrombocythaemia myelofibrosis (PET-MF) within starting dose category.

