M. Data Display Characteristics

Data displays produced for this study will include two types - summary tables, and data listings. Unless stated otherwise, data listings will be produced for all recorded data. Summary tables will include columns for each starting dose category and each type of myelofibrosis (MF) within the starting dose category, and the ordering of these diseases will be defined in the tables, listings, and figures (TLF) shells document. Summary tables will be produced as specified in the following sections. Additional data listings will be produced for outcome measures that involve extensive procedures to derive the analyzed outcomes.

Data listings will simply list the data that are either recorded on the CRF or derived for each patient. In general, they will be ordered by starting dose category, type of myelofibrosis (MF), patient number, and time of assessment, unless otherwise specified in the display shell. When expedient, additional levels of ordering hierarchy may reflect subsets of assessments within patient. Data listings will not display patient initials.

Summary tables will display summary statistics calculated for each starting dose category and each type of myelofibrosis (MF), and for all patients combined, unless described otherwise in the following sections, or in the display shells. For most summary tables, the types of myelofibrosis (MF) will be presented in separate columns, and the summary statistics of interest will be presented in rows.

Descriptive statistics (sample size, arithmetic mean, standard deviation (SD), median, minimum, maximum) will be calculated for quantitative safety data as well as for the differences from baseline, when appropriate. Counts and percentages will be presented for categorical data.

VII. Patient Accountability

A. Patient Characteristics

Demography. Data collected about the following patient characteristics at the screening/baseline visit will be listed and summarized for the safety population:

CCI

Disease History. Baseline history will be summarized and listed.

CCI

Medical History. Medical Histories will be listed.

Prior Disease Treatment. Data from prior disease treatments will be summarized and listed:

CCI

B. Disposition

Disposition. Patient disposition data will be summarized for the Safety Population by the type of myelofibrosis (MF). Summaries will include:

CCI

C. Protocol Deviations

Protocol deviations and waivers will be provided in a listing.

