The safety and tolerability of IMG-7289 will be assessed by the analysis of adverse events (AEs), as well as changes in physical examinations, vital signs, and laboratory values as detailed below, using the Safety Population.

A. Exposure

The summary will be presented by disease type (PMF, PPV-MF, and PET-MF) within the starting dose category and include the following:

The summary by patients:

- Summary of patient weekly IMG-7289 dose during initial treatment phase

All exposure data will also be listed by starting dose category, disease type (PMF, PPV-MF, and PET-MF) and patient.

B. Adverse Events

The AEs reported on the eCRFs will be coded using the latest version of MedDRA available to the sponsor at the time of study initiation (up-versioning will not occur), associating lower-level terms with preferred terms and system organ classes (SOC) by the primary hierarchy. The tables will display counts and percentages of patients who reported at least one AE in each system organ class represented in the AE data. Within each system organ class, the tables will

display the counts and percentages of patients reporting at least one AE, as designated by the preferred terms.

In the summary, if a causal relationship is considered probable, possible, or definite by the Investigator, the AE is considered to be “related”; while, if a causal relationship is considered remote/unlikely or unrelated, the AE is considered “unrelated”.

[figure not shown]
Severity of AEs will be reported using the NCI CTCAE grades (v4.03): Grade 1 - Mild, Grade 2 - Moderate, Grade 3 - Severe, Grade 4 - Life-Threatening, and Grade 5 - Fatal.

In any given category (e.g., SOC or preferred term) a patient will be counted only once. If a patient has the same AE on multiple occasions, only the highest toxicity grade will be used. Similarly, only the most related event will be used. For summaries of related events by toxicity grade, if a patient has the same AE with both “related” and “unrelated”, only the highest toxicity grade of the related event will be used. Percentages will be based on the number of patients in the subgroup of patients being tabulated and not the number of events. Summaries that are displayed by system organ class and preferred terms will be ordered by descending order of incidence of system organ class and preferred term within each system organ class.

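### Crude AE percentages are not comparable across starting-dose columns, because planned ITP exposure is 85 days in one column and 169 in the others and ATP exposure is open-ended in all

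*SAP*

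**What the plan says.** Safety and tolerability is a primary objective and endpoint (SAP II.A and III.A). SAP IX.B sets the numerator, "In any given category (e.g., SOC or preferred term) a patient will be counted only once", and the denominator, "Percentages will be based on the number of patients in the subgroup of patients being tabulated and not the number of events". Together these give a crude incidence proportion, without regard to time on drug. AEs count from first dispensing until 28 days after the last treatment.

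SAP VI.M defines the layout: "Summary tables will include columns for each starting dose category and each type of myelofibrosis (MF) within the starting dose category". SAP VI.L ties starting dose to study phase: "Categories for starting dose are: Phase 1/2a - 0.25 mg/kg/d (amendments 1, 2 and 3); Phase 2b - 0.5 mg/kg/d (amendments 4, 5"), with 0.6 mg/kg/d under amendment 6 also in Phase 2b.

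SAP IV.A gives the planned durations: "Patients enrolled in the Phase 1/2a portion of study are treated in the ITP daily for 85 days" and "Patients enrolled in the Phase 2b portion of study are treated in the ITP daily for 169 days". One ATP adds 85 days in Phase 1/2a, after a brief washout, and 169 days in Phase 2b. On repetition, Protocol 5.1.2 says: "The ATP is iterative and may repeat (ATP1, ATP2, etc".), for as long as the patient continues to qualify.

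The only item under the exposure summary in SAP IX.A is "Summary of patient weekly IMG-7289 dose during initial treatment phase". All exposure data will also be listed by patient.

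**The concern.** Starting dose is fully aligned with study phase, so a side-by-side AE table by starting dose is also a table by length of planned follow-up. A patient observed for longer has more opportunity to record at least one event. Two columns with the same underlying risk can therefore show different percentages, and a reader could take the gap for a dose effect on a primary endpoint.

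The SAP recognises this problem elsewhere. VI.J allows visit windowing where summaries would otherwise compare assessments made after unequal treatment time within a period. It names laboratory data, vital signs and symptom scores. The visible text gives AEs no such safeguard, and the exposure summary does not report treatment duration or any ATP time.

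**Working it through.** The documents give no AE rate and no calculation for this comparison, so there is no figure of the plan's own to reproduce. The hazard below is an assumption: constant, equal in every column, and varied through the percentage seen in the 85-day column.

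**Inputs.** Planned ITP of 85 and 169 days and ATP of 85 and 169 days (SAP IV.A). AE window of 28 days after last dose (SAP IX.B). 18 patients treated in Phase 1/2a out of about 75 (SAP IV.C), leaving about 57 for Phase 2b.

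**1. ITP only.** Windows are 85 + 28 = 113 days and 169 + 28 = 197 days, a ratio of 197/113 = 1.74. With P(t) = 1 − exp(−λt) and the same λ in each column, P_long = 1 − (1 − P_short)^(197/113).

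| 85-day column | 169-day columns | Ratio |
|---|---|---|
| 1% | 1.7% | 1.74 |
| 10% | 16.8% | 1.68 |
| 20% | 32.2% | 1.61 |
| 30% | 46.3% | 1.54 |
| 50% | 70.1% | 1.40 |
| 80% | 94.0% | 1.17 |

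As an example, at an assumed 0.5 events per year, 1 − exp(−0.5 × 113/365.25) = 14.3% and 1 − exp(−0.5 × 197/365.25) = 23.6%, a ratio of 1.65. At 0.25 and 1.0 per year the ratios are 1.69 and 1.57.

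**2. Early-onset events.** Suppose a share of the 169-day cumulative hazard falls in the first 28 days and the rest is spread evenly. On treatment days alone (85 against 169), with cumulative hazard from 0.1 to 1, the ratio is 1.25 to 1.40 for a share of one half, 1.08 to 1.13 for 80%, and 1.00 if all of it falls there.

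**3. ITP and ATP pooled.** These are ratios of AE windows, Phase 2b over Phase 1/2a, with the washout ignored. For rare events the percentages follow these ratios.

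| Assumed ATP uptake | Windows (days) | Ratio |
|---|---|---|
| One ATP for every patient | (338 + 28)/(170 + 28) = 366/198 | 1.85 |
| One ATP at 0.25 mg/kg/d, none elsewhere | 197/198 | 0.99 |
| Two ATPs at 0.25 mg/kg/d, none elsewhere | 197/(255 + 28) = 197/283 | 0.70 |
| One ATP in Phase 2b only | 366/113 | 3.24 |

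The documents do not give uptake. The visible text also does not say whether AE tables cover the ITP alone or all periods.

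**4. Effect of the remedy.** Under the same assumption, patients with a first event divided by patient-time at risk has an expected column ratio of 1.00, whatever the windows.

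**The case against.** Counting patients rather than events is the usual convention and is not itself an error. The study is open-label and not randomised, and the visible text specifies no AE test between columns. Patients are titrated individually. The titration rules changed between amendments, and the platelet target moved from 100–200 to 50–75 k/µL (Protocol 5.1), so equalising follow-up would not turn the columns into a dose comparison. The 0.25 mg/kg/d column is also imprecise: 2 of 18 patients is 11%, with an exact 95% interval of 1.4% to 35%. All of this stands. It limits the point to descriptive reading but does not remove the imbalance in follow-up.

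A reader might infer four stronger things that the documents do not support:

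- **That percentages differ about two-fold.** 169/85 = 1.99 is the ratio of treatment days. AE percentages would approach it only for rare events at a constant hazard with counting stopped at the last ITP dose, and SAP IX.B counts for 28 days more.
- **That the 0.25 mg/kg/d column will look safer.** Those patients may also enter repeating ATPs, and the pooled ratio can fall below 1.
- **That there is no person-time to correct with.** Per-patient exposure listings are planned. What the visible text lacks is a summary of duration.
- **That the SAP contains no adjusted AE display.** Text following the AE section is redacted and the table shells are in a separate document, so this cannot be asserted.

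**Conclusion.** The point holds as a limitation of a primary safety display. Crude AE percentages by starting dose are not comparable, because follow-up differs by design. For a full planned ITP with the 28-day window, the difference arising from time alone is about 1.2- to 1.7-fold, with a ceiling of 1.74 for rare events, and it is close to 1 for events that occur mainly in the first weeks. These figures rest on an assumed equal constant hazard, or the stated front-loaded one, and on every patient completing the planned ITP. With ATP time pooled, neither the size nor the direction can be stated from the documents. That is a reason to report exposure rather than evidence of bias in one direction. Because no between-column test is visible and one column has 18 patients, this is an inexpensive improvement that should be made, and it does not threaten a formal conclusion.

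**What to change.** Keep the crude tables. For the by-starting-dose display, add to SAP IX.B either or both of the following, unless the redacted AE table list already has them:

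- AE tables restricted to onset in ITP Days 0–84, the 85 days planned in every column.
- Exposure-adjusted incidence rates: patients with a first event per patient-time at risk, with the time at risk defined to include the 28 days after last dose.

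State for each AE table whether it covers the ITP only or all periods. Extend SAP IX.A to summarise total treatment duration, including all ATPs, by starting-dose column. This last change is needed whatever the redacted AE list contains.

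The cost is SAP wording and a few extra tables from data already collected. The common-window table omits later events, so the full-period tables are still needed. The rates are easiest to interpret when the hazard is roughly constant, so they complement the common window for early-onset events. The columns will still differ in titration rules and platelet target, and a footnote should say that they are descriptive and not a dose comparison.
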